5.9 Staff Training

5.9.1 Clinical trial training workshop at MRC/UVRI before start of trial

The trial coordinator, data managers, and all site staff will attend a 5-day clinical trial training workshop at MRC/UVRI in July/August 2019. The workshop will facilitate staff becoming knowledgeable about the trial protocol and procedures; data entry and data management; other standard operating procedures; ethical conduct of research; and ensuring privacy and confidentiality.

5.9.2 Site staff training on neonatal care and clinical guidelines before start of trial

The trial coordinator and the paediatricians, medical officers, and nurses at the 4 sites will attend an additional 5-day training on neonatal care and clinical guidelines at MRC/UVRI in July/August 2019. This training will facilitate staff members' proficiency in the following areas: KMC guidelines; standardised guidelines for common neonatal conditions; Ballard gestational age scoring; pulse oximetry monitoring and recording; and counselling parents/caregivers. Training will emphasise counselling parents/caregivers about the potential for mortality at the time of enrolment, as well as counselling parents/caregivers of neonates who die or have a life-threatening event and those who witness a death. Paediatricians and medical officers at KNRH and JH will also be trained in the acquisition of cranial ultrasound (cUS) images.

5.9.3 Refresher trainings throughout trial

The trial coordinator and site paediatricians will conduct regular quality improvement activities, including refresher training on KMC and standardised guidelines, throughout the duration of the trial.

6. Study Evaluations

6.1 Clinical Evaluations

6.1.1 Evaluations during first 24 hours

All participants will receive continuous monitoring and recording of HR and SpO₂, using a pulse oximeter, for 72h post-randomisation. Continuous monitoring will continue until participants no longer require any form of respiratory support.

Axillary temperature and respiratory rate will be manually measured every 6h for the first 24h. All participants will be evaluated at least once by a study paediatrician or medical officer during the first 24h post-randomisation. Blood glucose will be measured every 6h, unless <2.6 mmol/l in which case it will be measured hourly until 2 or more consecutive readings are in normal range (2.6 – 6.9 mmol/L).

6.1.2 Evaluations from 24 hours to hospital discharge

All participants will be followed at least daily while admitted to the hospital. Unless otherwise noted, the following data will be collected and recorded in eCRFs daily from 24h through day 7 of life, then weekly on days 14, 21, and 28. If participants are discharged prior to day 7, additional follow-up will be arranged according to study site (see Section 5.8 for additional details).

- a) Participants will receive monitoring of HR, SpO₂, respiratory rate, and axillary temperature every 6h until they meet stability criteria (see Section 3.2.5), after which the frequency of monitoring will transition to daily. Measurements will be recorded in eCRFs. Please refer to Section 8.1 for additional details on clinical monitoring.
- b) Daily review with the following data documented:
 - Date and time of starting to receive breast milk (may be given by nasogastric tube, spoon, syringe, etc)
 - Date and time of starting breastfeeding

- Date that full breast milk feeding is established
- Daily IV fluid volumes and drip rates
- Medications administered each day, including dosage and route of administration
- Therapies administered each day, including flow rate and mode of delivery for neonates receiving oxygen
- Daily measurement of blood glucose (may be discontinued once neonate is tolerating full enteral feeds)
- Compliance with the standardised management protocol and discussion of any deviations with the site paediatrician or medical officer
- Documentation about skin-to-skin contact:
 - Date and time of skin-to-skin contact initiation
 - Duration of skin-to-skin contact/day (hours and minutes) ○ Caregiver providing skin-to-skin contact
 - Whether skin-to-skin contact is temporarily discontinued and date/time of this event
- Documentation of any change in clinical condition warranting temporary cessation of intervention and date/time of temporary cessation
- Identification of any SAE
- Documentation of any reason to suspect mother and/or baby is infected with SARS-CoV-2 (based on signs/symptoms or testing status) for babies recruited after 25 March 2020

c) Weighed on day 5, then daily until discharge (unless deemed too unstable by site study staff); weighing to be in clustered with other activities (e.g., diaper changes)

d) OFC and length will be measured weekly using study-specific equipment

e) For participants at KNRH and JH, cranial ultrasounds (cUS) will be performed on days 1, 3, and 7 of the hospitalisation, or as an outpatient if discharged before day 7 (see Section 6.1.6 for additional details)

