Defined as $\text{SpO}_2 < 88\%$ in oxygen AND ≥ 1 of:

- Respiratory rate < 20 or > 100 breaths/min
- Apnoea requiring bag-mask ventilation
- HR < 100 or > 200 bpm

Major congenital malformation:

A malformation that is present at birth and which is incompatible with life or requires immediate surgical management

Severe jaundice:

Jaundice occurring within the first 24h after delivery and/or visible in sclera, palms or soles

PRIMARY OUTCOME

Early neonatal mortality:	Death of a neonate within the first 7 days after birth (day 0-6)
----------------------------------	--

SECONDARY OUTCOMES

Hypothermia:	Axillary temperature below the normal range (36.5°C – 37.5°C); can be subcategorised as follows: Mild: 36.0°C – 36.4°C Moderate: 32.0°C – 35.9°C Severe: <32°C
---------------------	---

Duration of hospital admission:	Mean time (days and hours) from hospital admission to discharge
--	---

Breastmilk feeding:	Process of feeding a mother's breastmilk to her infant, either directly from the breast or by expressing milk from the breast and feeding it to the infant by nasogastric tube, bottle, cup, or spoon, to provide calories, macronutrients, and micronutrients (10)
----------------------------	---

Time from intervention/control procedures starting to exclusive breastmilk feeding:	Mean time (days and hours) from initiation of intervention/control procedures to exclusive breast milk feeding
--	--

Neonatal mortality:	Death of a neonate within the first 28 days of life
----------------------------	---

Time from intervention/control procedures starting to clinical stabilisation:	Mean time (days and hours) from initiation of intervention/control procedures to clinical stabilisation, with stability defined as having met the following criteria for a continuous period of at least 24h: (i) Breathing spontaneously with SpO ₂ >90% in room air (ii) No need for supplemental oxygen or CPAP (iii) Respiratory rate 40 to <60 breaths per minute (iv) No apnoea (v) Heart rate 80 to <180 beats per minute (vi) Axillary temperature 36.0 to 37.4 degrees Celsius (vii) No need for IV fluids
--	---

Time from intervention/control procedures starting to death:	Mean time (days and hours) from initiation of intervention/control procedures to death
---	--

Frequency of readmission:	Mean frequency of episodes in which an infant who had been discharged from a hospital is admitted again during a defined time period

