Daily weight gain:	Mean daily weight gain (g/day) during a defined time period
Infant-caregiver attachment:	Assessed using the Maternal Infant Responsiveness Instrument (MIRI), a 22-item questionnaire measuring maternal responsiveness to infant cues (11,12); initially developed in the United States and being used in Uganda
Women's well-being:	Assessed using the Women's Capability Index (WCI), a composite measure of quality of life that will capture the broader benefits to the mother of practising KMC compared to standard care (13); originally developed in Malawi, and now being adapted and tested for use in Uganda

OTHER PROCESS OUTCOMES

Cardio-respiratory stability:	Proportion of time spent with suboptimal HR (<100bpm) and SpO ₂ (<85%) over the first 24h post-randomisation, measured and recorded continuously using pulse oximetry.
Hypothermia density:	Proportion of time temperature <36.5°C during a defined time period
Presence and severity of intraventricular haemorrhage (IVH):	Complication of prematurity characterised by bleeding within the ventricles (fluid-filled areas) inside the brain, typically originating from the periventricular germinal matrix (a highly vascular collection of neuronal-glial precursor cells); majority of affected infants are asymptomatic; diagnosis is based on screening cranial ultrasound; severity ranges from grade 1 (mild) to grade 4 (severe) (14)
Presence of late intracerebral sequelae of prematurity:	Late intracerebral sequelae of prematurity may include, but are not limited to the following: cystic degeneration, cerebral atrophy, post-haemorrhagic hydrocephalus
Hypoglycaemia:	Blood glucose level <2.6 mmol/L, as measured by bedside testing

Executive Summary

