2.4 Formative Work

A study demonstrating the feasibility of KMC initiated prior to stabilisation amongst neonates $\leq 2000\text{g}$ was undertaken at Jinja Regional Referral Hospital in Uganda in 2016, led by [name] ([name]). The findings, which are summarized below, were published in the *Journal of Global Health* in 2018 (56).

Finding 1: Sufficient numbers of neonatal admissions met eligibility criteria: To determine the number of eligible neonates, audit data were collected on neonates admitted between June 2015 and May 2016. We also reviewed current practices to inform coding of neonates as ‘before stabilisation,’ i.e., for whom the indication for KMC is currently “uncertain.” A total of 268 charts were reviewed, among which 254 met birthweight criteria and were complete. Amongst these, 226 (89%) were receiving ≥ 2 care therapies (Table 1). Among neonates who received only one therapy, the majority received empiric antibiotics because they were at risk of infection (i.e., not given for suspected or confirmed infection), a common practice in preterm/LBW neonates and frequently given to newborns considered stable. For

this reason, this enrolment criterion has been modified to receipt of ≥ 1 therapy excluding empiric antibiotics. Hence based on admission data in JH showing ~ 480 neonates ≤ 2000 g, we anticipate ≥ 400 admissions to be eligible each year at JH (see Section 10.1 for information on other sites).

Table 1: Number of care therapies received amongst neonates in admissions audit (N=254)

Number of therapies received*	Frequency (%) of ≤ 2000 g neonates N=254	95% CI	Frequency (%) of < 1500 g neonates n=110	95% CI	Frequency (%) of < 1000 g neonates n=29	95% CI
0 to 1	29 (11.4)	7.8-16.0	11 (10.0)	5.1-17.2	3 (10.3)	2.2-27.4
2	73 (28.7)	23.3-34.7	32 (29.1)	20.8-38.5	4 (13.8)	3.9-31.7
3	105 (41.3)	35.2-47.7	47 (42.7)	33.3-52.5	19 (65.5)	45.7-82.1
4 to 5	47 (18.5)	13.9-23.8	20 (18.2)	11.5-26.7	3 (10.3)	2.2-27.4

*Oxygen, IV fluids, phenobarbital, antibiotics (empiric or for presumed/confirmed infection)

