3.2.5 Clinical Stability Criteria

Neonates will be considered stable when the following criteria have been met for a continuous period of at least 24h [criteria consistent with the WHO I-KMC trial (61)]:

- (i) Breathing spontaneously with $\text{SpO}_2 >90\%$ in room air
- (ii) No need for supplemental oxygen or CPAP
- (iii) Respiratory rate 40 to <60 breaths per minute
- (iv) No apnoea
- (v) HR 80 to <180 beats per minute
- (vi) Axillary temperature 36.0 to 37.4 degrees Celsius
- (vii) No need for IV fluids

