6.3.1 Understanding causal pathways for clinical effects

Understanding the causal pathways for clinical effects of the intervention (Objective 2) will be achieved by measurement of the following process outcomes, which are categorised as providing very early (within 24 hours), early (within 72 hours), or late clinical impact:

Very early impact:

- Cardio-respiratory stability within 24 hours post-randomisation
- Prevalence of hypothermia within 24 hours post-randomisation
- Hypothermia density within the first 24 hours post-randomisation
- Prevalence of hypoglycaemia within 24 hours post-randomisation

Early impact:

- Cardio-respiratory stability within 72 hours post-randomisation
- Prevalence of hypothermia within 72 hours post-randomisation
- Hypothermia density within the first 72 hours post-randomisation
- Prevalence of hypoglycaemia within 72 hours post-randomisation
- Presence and severity of IVH within 72 hours post-randomisation

Late impact:

- Presence and severity of IVH at day 7
- Proportion of neonates exclusively breastmilk feeding at discharge
- Presence of late intracerebral sequelae of prematurity (e.g., hydrocephalus, cystic degeneration) at day 28-30

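### After 24 h the temperature schedule depends on clinical stability, so hypothermia detected by 72 h may differ very slightly by arm; a minor point with a cheap fix

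*Protocol*

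**What the plan says.** Section 6.1.1 has axillary temperature read 6-hourly in every baby for the first 24 h. From then on, section 6.1.2 prescribes "axillary temperature every 6h until they meet stability criteria (see Section 3.2.5), after which the frequency of monitoring will transition to daily". Table 2 in section 8.1 agrees: 6-hourly in unstable babies, daily in stable ones, in both arms.

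Stability (section 3.2.5) must hold "for a continuous period of at least 24h". It includes "Axillary temperature 36.0 to 37.4 degrees Celsius", together with criteria on oxygen saturation, respiratory support, respiratory rate, apnoea, heart rate and IV fluids.

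The Definitions give hypothermia as "Axillary temperature below the normal range (36.5°C – 37.5°C" and label 36.0-36.4 °C mild. Hypothermia density is "Proportion of time temperature <36.5°C during a defined time period".

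Section 6.3.1 lists "Prevalence of hypothermia within 72 hours post-randomisation" and density over the same 72 h among the early-impact process outcomes. It gives no formula for the prevalence measure. Section 1.4.2 makes time to clinical stabilisation a secondary outcome.

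**The concern.** After 24 h, how often a baby's temperature is read depends on a status reached after randomisation, and the trial itself treats the time to that status as something KMC may alter. Being stable does not rule out the event, because the stability band overlaps the mild hypothermia band. Of two babies with identical temperatures, the one who stabilises sooner is read less often and is less likely to be caught below 36.5 °C.

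No other temperature source common to both arms covers 24-72 h. The loggers in section 8.1 run for the first 24 h in about 5% of babies. Heart rate and oxygen saturation, by contrast, are recorded in all babies "using a pulse oximeter, for 72h post-randomisation".

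At stake is the reading of one exploratory measure of thermal control, which section 2.1 names among the causal pathways for KMC. The efficacy conclusion is not at stake.

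**Working it through.** The protocol states no figure for 72 h hypothermia, so there is none to reproduce.

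**1. Scheduled readings to 72 h** (sections 6.1.1 and 6.1.2)
- Not stable by 72 h: 6, 12, ..., 72 h = 12 readings.
- Stable at 48 h: 6-hourly to 48 h (8 readings) plus one at 72 h = 9 readings.
- Stable at 24 h, the earliest possible: 6, 12, 18, 24, 48 and 72 h = 6 readings.

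**2. How early can stability come?** It needs 24 continuous hours off oxygen, CPAP and IV fluids, so a baby stable at 24 h would have been off all three from about randomisation. In the audit (section 2.4), "226 (89%) were receiving ≥ 2 care therapies"; Table 1 shows 29/254 = 11.4% on 0 or 1. That 11.4% overstates the group at risk: most one-therapy babies were on empiric antibiotics, which no longer qualify for entry, and babies on no therapy are excluded (section 4.2.2). The 10 feasibility babies averaged 3.7-4.1 therapies per day over 14 days. The working case is therefore stability at 48 h.

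**3. Loss of detection, 12 v 9 readings.** Assumptions, none of them from the protocol:
- First-order autoregressive normal temperatures every 6 h, rounded to 0.1 °C.
- Mean 36.5, 36.7 or 36.9 °C; SD 0.3, 0.4 or 0.5; 6-h correlation 0, 0.4 or 0.8. This gives 27 scenarios of 400,000 babies each.
- Stable at 48 h means that all readings from 24 to 48 h lie in 36.0-37.4 °C. The other stability criteria are not modelled.

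The share with any reading below 36.5 °C falls by 0.6-10.0 points (median 4.3). At mean 36.7, SD 0.4 and correlation 0.4 it falls from 93% to 88%. A repeat run gave the same values to within 0.1 point.

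**4. False arm difference** = loss × arm gap in the share stable at 48 h, with no true thermal difference.
- 5-point gap: 0.05 × 0.6 = 0.03 to 0.05 × 10.0 = 0.5 points.
- 10-point gap: 0.10 × 0.6 = 0.06 to 0.10 × 10.0 = 1.0 points.

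Cross-check with independent readings, each with probability q of being below 36.5 °C: loss = (1 − q)^9 − (1 − q)^12. For q of 2%, 5%, 10% and 20%, a 10-point gap gives 0.49, 0.90, 1.05 and 0.65 points.

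**5. Scale.** With 1094 per arm (section 10.1) and an assumed prevalence of 70%, the standard error of the arm difference is √(2 × 0.7 × 0.3 / 1094) = 0.0196, about 2.0 points. The largest false difference is therefore about half a standard error. If no baby is stable before 72 h, it is zero.

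**6. Density.** This mainly loses precision. On the sparsest schedule (6 v 12 readings), a plain share of readings over 0-72 h shifts by −3.2 to +0.4 points because it overweights day 1. Weighting each of the first four readings by 6 h and each of the last two by 24 h reduces the shift to −0.2 to +1.1 points.

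**The case against.** The strongest reply is that section 6.3.1 does not define 72 h prevalence, and section 10.2.2 refers to a separate analysis plan that could score only common time points. Every baby still in hospital has 6-hourly readings to 24 h and at least daily readings after that, so nothing in the protocol prevents this. That is right as far as it goes: the differential detection can be removed in analysis. But the reading schedule is fixed in the protocol, and no analysis plan can recover readings that were never taken.

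A second reply is that Table 2 is a clinical minimum. A baby who destabilises could return to 6-hourly checks, and sparing stable babies extra handling is reasonable in busy units. This also stands. It lowers the size further and is a genuine, if small, cost of the remedy.

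Three stronger readings are tempting, and the documents do not support them.
- A reader might compare 6 with 12 readings and infer a large bias. That contrast applies only to babies stable at 24 h, who should be very rare (step 2), so those losses should not be used.
- A reader might infer that the error favours KMC. That holds only if KMC shortens stabilisation, which the trial is testing; if KMC lengthens it, the sign reverses.
- A reader might infer that the stability and hypothermia bands contradict each other. They serve different purposes, and the overlap matters here only because it governs step-down.

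**Conclusion.** The point holds as a minor, cheap improvement. If 72 h prevalence means any reading below 36.5 °C, the protocol's schedule makes detection depend on time to stabilisation. For a 5-10 point arm gap in babies stable at 48 h, the false difference is about 0.03-1.0 points, in either direction, against a standard error of about 2 points.

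That size rests on assumed temperature distributions, an assumed arm gap and an assumed prevalence; the protocol gives neither a temperature distribution nor the share stable before 72 h. The mechanism is certain from the text. Its size is uncertain, and may be nil.

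Mortality, the sample size and all 24 h hypothermia outcomes are untouched, because every baby has the same schedule in the first 24 h.

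**What to change.** In section 6.1.2 and Table 2, take axillary temperature every 6 h to 72 h post-randomisation in every baby still in hospital, whatever its stability, clustered with other care, then daily if stable. All such babies then have 12 scheduled readings, and the schedule-driven difference disappears among those alive and in hospital. The cost is one sentence, one table cell, and slightly more handling: 12 − 9 = 3 extra readings for a baby stable at 48 h, at most 12 − 6 = 6, and none for a baby not stable by 72 h.

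If that is not adopted, score 72 h prevalence only at the time points scheduled for all babies (6, 12, 18, 24, about 48 and 72 h) and time-weight density. This needs no extra readings but loses sensitivity: detected prevalence falls by 2.4-24.5 points in the same scenarios, equally in both arms when temperatures are equal. The stability definition should stay as it is.

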6.1.3 Evaluations in event of clinical deterioration

Study staff at all sites will be trained to recognise signs of severe illness according to adapted possible serious bacterial infection (aPSBI) criteria (Figure 2a) and to inform study staff if a participant meets any of these criteria. The study paediatrician or medical officer (or study nurse if neither is present) will then examine the neonate as soon as possible to assess whether signs of early-onset (<72h of age) or late-onset (≥ 72 h of age) infection (Figure 2b) are present. Neonates will be reassessed for signs of severe illness and infection during daily rounds. Where available, a blood culture will be obtained as soon as possible if a neonate meets criteria for suspected infection; however, this will not delay administration of antibiotic therapy. The site paediatrician (or medical officer, if paediatrician not present) will direct management in accordance with standardised clinical guidelines, including starting CPAP if this is local standard of care. The paediatrician or medical officer will then complete the appropriate safety monitoring documentation. Study staff will also assess if the neonate meets criteria for temporary withdrawal from the intervention arm (see Section 9). At the discretion of the study paediatrician and in line with current neonatal unit policies at each site, neonates may be referred to a higher-level facility for more specialised care; however, existing data indicate that this is an uncommon occurrence.

Figure 2a. Screening criteria for severe illness

Newborn unit staff to inform the study team as soon as possible if any of the following are present:

- Refusal to feed, feed intolerance or abdominal distension (after starting to feed)
- Lethargic (unresponsive or responsive only with tactile stimulation)
- Respiratory rate >80 breaths/min or severe chest wall in-drawing or new oxygen/CPAP requirement - Apnoea (new onset and/or persistent)
- Seizures
- Axillary temperature >37.5 degrees Celsius
- Axillary temperature <35.5 degrees Celsius (after 1h of observed skin-to-skin contact, not associated with environment or with hypoglycaemia)

Figure 2b. Additional criteria for investigation of suspected early- or late-onset infection amongst neonates screened positive for signs of severe illness

Obtain blood culture if criteria for severe illness met, plus 1 of:

- Axillary temperature >37.5 degrees Celsius
- Axillary temperature <35.5 degrees Celsius (after 1h of observed skin-to-skin contact) - Jaundice
- Apnoea (new onset and/or persistent)
- Hepatomegaly
- Pallor
- Lethargy (unresponsive or responsive only with tactile stimulation)

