5.7.2 Delivering the control arm

Neonates allocated to the control arm will be placed in an incubator or under a radiant heater, as per standard management at the study sites. They will wear a hat and be wrapped as per standard care. Oxygen will be provided from an oxygen cylinder or concentrator and IV fluids will be securely attached via an IV cannula with drip rate calculated, as in the intervention arm. The pulse oximeter will be placed inside the incubator or next to the radiant heater. The parent/caregiver will be able to touch the baby, if

requested, but will not provide any skin-to-skin contact until he/she meets clinical stability criteria (see Section 3.2.5), which are consistent with those used in the WHO I-KMC trial and in line with standard clinical procedures at the study sites. Once stable, the baby can transition to routine (intermittent) KMC with the parent/caregiver in a chair or bed in the study area.

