14.3 Evaluation of risks and benefits

14.3.1 Potential risks or benefits of standard care in Uganda

Incubators are the standard alternative to KMC for maintaining normothermia in preterm and low birthweight neonates. In resource-limited facilities such as the four trial hospitals, it is common for several neonates to share one incubator or radiant heater. In this trial, neonates randomised to the control group will receive standard care. Risks associated with standard care with an incubator or radiant heater include hypothermia (40,76); hyperthermia (77); nosocomial infections, related to lack of effective cleaning standards (78–80); and cross-infection from other neonates when incubators are shared, a common practice in low-resource facilities. Failure of incubators/heaters to properly regulate temperature may be related to malfunction (e.g., over- or under-heating) (77,80–83), loss of electrical supply (51), ignorance of how to regulate set-points (77), as well as environmental factors (81). In lowresource hospitals, where there may be few nurses and doctors available, neonates nursed in incubators/heaters may not be monitored well, and illness or serious events (e.g., apnoea) may not be detected in time. Such events may be detected more rapidly when neonates are in the KMC position with their mother (or another caregiver). Further, due to high purchase cost and poor routine maintenance practices, hospitals in low-resource settings commonly face shortages of functional incubators (50–52,84).

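### The low-temperature sign in Figures 2a and 2b requires 1 h of skin-to-skin contact, so a cold control who is not yet stable cannot meet it as written

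*Protocol*

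**What the plan says.** Section 6.1.3 trains staff to recognise signs of severe illness and to "inform study staff if a participant meets any of these criteria". Nothing restricts this to the KMC arm. Figure 2a has seven signs, and the low-temperature one is "Axillary temperature <35.5 degrees Celsius (after 1h of observed skin-to-skin contact, not associated with environment or with hypoglycaemia".

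Figure 2b then gives the culture rule: "Obtain blood culture if criteria for severe illness met, plus 1 of" of seven further signs. Its low-temperature sign is "Axillary temperature <35.5 degrees Celsius (after 1h of observed skin-to-skin contact", without the exclusions for environment and hypoglycaemia.

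For controls, section 5.7.2 says the caregiver "will not provide any skin-to-skin contact until he/she meets clinical stability criteria". Section 3.2.5 requires all stability criteria to hold for at least 24 h continuously, and one of them is "Axillary temperature 36.0 to 37.4 degrees Celsius". Controls may start intermittent KMC only after that (section 3.2.4).

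**The concern.** The trial is unblinded at the bedside, so a written trigger for alerting the study team or taking a culture should ask the same thing of both arms. This one depends on receiving the experimental intervention. An infant below 35.5 °C in an incubator may be as ill as one at the same temperature on the mother's chest, but only the second has a route to meeting the sign.

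Two things are at stake: equal formal safety notification, and equal work-up for suspected infection. There is also a possible indirect effect on the laboratory information used to assign causes of death (section 8.5). The protocol itself names hypothermia as a risk of incubator and heater care (section 14.3.1), so the sign is unavailable in a setting where cold is expected.

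**Working it through.** The protocol states no figure to reproduce here. The check is to set the passages side by side.

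**Step 1. Can a not-yet-stable control meet the sign?** The parenthesis has two possible readings.
- *The infant has already been in contact for 1 h.* Section 5.7.2 rules this out before stability.
- *Rewarm by contact for 1 h, then recheck.* Section 5.7.2 rules this out as well.

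An infant below 35.5 °C is outside the 36.0 to 37.4 °C band, so is not accumulating the 24 h needed for stability. On either reading the sign can be met only by breaching allocation.

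**Step 2. Is there an equivalent elsewhere?** Sections 6.1.1, 6.1.2, 7.2, 8.1, 8.3 and 9.1 contain no incubator or radiant-heater version of the sign. The high-temperature sign (>37.5 °C) has no contact condition, so the asymmetry is confined to cold.

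**Step 3. What differs on a literal reading?** Take an infant below 35.5 °C, the cold not being due to environment or hypoglycaemia. Compare a KMC infant after 1 h of contact with a not-yet-stable control.

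| Other signs present | Notification (2a) | Culture rule (2b) |
|---|---|---|
| None | KMC only | KMC only if one sign may serve both figures; otherwise neither |
| Only feeding, respiratory or seizure signs (in 2a, not 2b) | Both arms | KMC only |
| Only jaundice, hepatomegaly or pallor (in 2b, not 2a) | KMC only | KMC only |
| Only lethargy, or only apnoea (in both figures) | Both arms | Both arms if one sign may serve both figures; otherwise KMC only |

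Whether a single sign may satisfy both figures is not stated, which leaves the first and last rows open for culture.

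**Step 4. What depends on the sign?** Suspected infection and blood culture are not among the outcomes in sections 1.4.1, 1.4.2 or 6.3.1. The hypothermia outcomes rest on temperature measurement, not on these figures. The protocol gives no frequency of readings below 35.5 °C, so the number of infants affected cannot be calculated.

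**The case against.** The strongest case against is that little follows in practice, and most of it stands.

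- **Other provisions cover a cold control.** Axillary temperature is taken every 6 h before stability in both arms, there is daily reassessment for severe illness and infection, and section 8.3 sends any abnormal finding by study staff to the site paediatrician or medical officer with no contact condition. Section 7.2 says the units have procedures for hypothermia and sepsis. These protect the individual infant, but none supplies a control-arm version of the trigger.
- **Treatment is not gated.** "Where available, a blood culture will be obtained as soon as possible if a neonate meets criteria for suspected infection", and section 6.1.3 says that antibiotics are not to be held up for it. A reader might infer that cold controls go untreated or receive fewer antibiotics; the protocol does not support that.
- **Staff may simply disregard the contact clause for controls.** The trigger would then be looser for controls than for KMC infants, who would still need 1 h of contact. In Figure 2a the environment and hypoglycaemia exclusions would still apply to controls; only Figure 2b lacks them. Because the asymmetry can run either way, a reader who infers bias in a known direction goes beyond the text.
- **The contrast is not purely by arm.** KMC infants go to an incubator or heater during breaks and temporary withdrawal (sections 5.7.1 and 9.1). Median contact in the feasibility study was 4.5 to 9.7 h per day (section 2.4), which is 4.5/24 = 19% to 9.7/24 = 40% of the day. If prior contact is required, many KMC readings would not qualify either. This narrows the difference and shows that the condition fits neither arm well.

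**Conclusion.** The point holds as a minor defect of wording that should be corrected. Followed as written, one of seven signs in each figure is closed to controls until they are stable, and the protocol offers no substitute. The result is unequal formal notification and infection work-up between unblinded arms, of unknown size and uncertain direction.

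A reader might infer that mortality, hypothermia or another listed outcome is ascertained differently by arm. The protocol does not support this: no listed primary, secondary or process outcome runs through these figures. Cause-of-death review uses all laboratory information, and blinding the reviewers does not replace a culture that was not taken. Any effect there is only a possibility.

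The conclusion rests on a literal reading of the parenthesis and on this protocol alone. The standardised clinical guidelines and site procedures are not shown and may contain a workable equivalent.

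**What to change.** In both figures, replace the contact condition with: *<35.5 °C persisting on recheck after 1 h of observed warming by the method in use at the time (skin-to-skin contact, or a functioning incubator or radiant heater)*.

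- *Method in use at the time* also covers KMC infants in a warmer during a break or temporary withdrawal.
- *Functioning* is needed because section 14.3.1 notes: "Failure of incubators/heaters to properly regulate temperature may be related to malfunction".
- Keep the environment and hypoglycaemia exclusions in Figure 2a.
- State that the recheck does not delay clinician review or treatment of an infant who causes concern. Otherwise the new wording could build in a 1 h wait.

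The clinical team should confirm the wording. The cost is an edit to two figures, a training note, and at most one extra axillary reading in an infant already found cold. No new equipment is needed.
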